4. To gain analytical power, a general rule of thumb is that 10-20 observations should be used for estimating a parameter [12]. If the number of covariates after steps 2 and 3 is more than 10, the distributions of the remaining covariates will be compared by intervention group to select the potential confounders associated with baseline imbalances.

Multiple imputation will not be performed in the individual-level covariate adjusted regression model. The estimates of treatment effect will be compared between the regression models with and without the individual-level covariate adjustment to assess the robustness of the conclusion drawn from the primary analysis.

Subgroup analyses for sex (Male, Female), age (18 – 54 years, 55 years or greater), race (Black, White, Other) and ethnicity (Hispanic or Latinx, Not Hispanic or Latinx) will be performed as required by the NIH [13]. Responses of “Unknown,” “Don’t know” and “Refused to answer” will not be analyzed. These subgroup analyses will utilize the same mixed-effect model as for the primary outcome analysis, but with the inclusion of an interaction term between treatment arm and the demographic subgroup. Contrasts will be used to test for statistically significant differences in the primary outcome hypothesis by subgroup.

An analysis using the Per Protocol (PP) population will be performed using the same methods as described in Section 7.2.2. This population will exclude participants who had appointments with PCPs in the opposite treatment arm or had deviation from the protocol in terms of intervention exposure including the participants who were shown the wrong video doctor. No multiple imputation will be conducted for the PP population.

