9.0 SIGNIFICANCE TESTING AND MULTIPLICITY

The primary outcome will be evaluated using a two-sided test with a type I error rate of 5%. There are several secondary outcomes; however, adjustments for multiple comparisons will not be performed since these are not part of the study's primary objective. The resulting p values will be interpreted appropriately in the context of the multiple tests being performed. Effect estimates will be presented with confidence intervals, and interpretation of hypothesis tests for multiple secondary outcomes will take into consideration the number of tests that were performed. Reporting of results will be transparent, with null as well as significant findings reported.

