Table 6 shows power for the two outcomes in the four simulated scenarios described above, under four conditions (A-D) of number of PCPs and patient participants per PCP.

Condition A shows the power for the original situation of 60 PCPs and 8 participants per PCP, with Conditions B and C illustrating the impact to power when keeping the number of PCPs at 60 but reducing the number of participants per PCP to 4 or 5. As a sensitivity analysis, we also examined the situation in which 50 PCPs had 4 participants each (Condition D), which we believe is a worst case scenario in which less than 60 PCPs are contributing patients and those that do have participants enrolled from their panel have fewer than the expected 5.

Effect of time trends of the intervention effect and possible assessment impact in the control group: The additive treatment effect for the 180-day period is the sum of the 90-day additive effects for the two 3-month time intervals. For example, Scenario 1 indicates 90-day means of 20 and 14 in the two groups at both the 3- and 6-month time points, which translate into 180 day means of 40 and 28 in the two groups, so a treatment effect of -12 days. In scenarios 2 and 4, the waning of the effect causes this outcome to lose power. The scenarios with assessment impact have more power because there is higher power for lower control group mean values due to lower variability of the binomial distribution for a lower probability parameter (and because we are assuming equal assessment impact between the two groups). If the impact were higher in the control group, the treatment effect would be reduced, reducing power.

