² Results for the treatment effect are obtained from the mixed effects negative binomial model adjusted for site (stratification factor) and baseline value of the response, [*list of all covariates included in the model*] are adjusted. Missing values from the variables of the response and covariates are not imputed.

³ The rate ratio is defined as the exponentiated estimate of the treatment effect as a ratio of the mean total number of days of risky opioid use for those enrolled to STOP versus EUC within the first 180 days post-baseline.

Table 36: Summary of Primary Outcome Analysis by Sex and Treatment Arm

Subgroup	Number of Participants Enrolled	Treatment Arm		Results ¹			
		EUC (N=)	STOP (N=)	Results ¹			
		Days of Risky Opioid Use in the 180 Days from Baseline (Mean (SD))	Days of Risky Opioid Use in the 180 Days from Baseline (Mean (SD))	Rate Ratio	95% Lower Confidence Limit	95% Upper Confidence Limit	p-value
Male	N	X.X (X.XX)	X.X (X.XX)	X.XX	X.XX	X.XX	0.xxx
Female							

¹ Results are obtained from the mixed effects negative binomial model. The rate ratio and p-value for the interaction term between treatment arm and subgroup is shown. Missing values are not imputed.

Table 37: Summary of Primary Outcome Analysis by Age and Treatment Arm

Subgroup	Number of Participants Enrolled	Treatment Arm		Results ¹			
		EUC (N=)	STOP (N=)	Rate Ratio	95% Lower Confidence Limit	95% Upper Confidence Limit	p-value
		Days of Risky Opioid Use in the 180 Days from Baseline (Mean (SD))	Days of Risky Opioid Use in the 180 Days from Baseline (Mean (SD))				
< 55 years	N	X.X (X.XX)	X.X (X.XX)	X.XX	X.XX	X.XX	0.xxx
≥ 55 years							

¹ Results are obtained from the mixed effects negative binomial model. The rate ratio and p-value for the interaction term between treatment arm and subgroup is shown. Missing values are not imputed.

Table 38: Summary of Primary Outcome Analysis by Race and Treatment Arm

Subgroup	Number of Participants Enrolled	Treatment Arm		Results ¹			
		EUC (N=)	STOP (N=)				
		Days of Risky Opioid Use in the 180 Days from Baseline (Mean (SD))	Days of Risky Opioid Use in the 180 Days from Baseline (Mean (SD))	Rate Ratio	95% Lower Confidence Limit	95% Upper Confidence Limit	p-value
Black	N	X.X (X.XX)	X.X (X.XX)	X.XX	X.XX	X.XX	0.xxx
White							
Other ²							

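### SAP Tables 36-39 report the treatment-by-subgroup interaction under a plain 'Rate Ratio' heading, and no model-based STOP/EUC rate ratio within any subgroup is planned

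*SAP*

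**What the plan says.** SAP 7.4 plans subgroup analyses of the primary outcome by sex, age (two bands), race (three groups) and ethnicity. The model is the primary mixed-effects negative binomial model, "but with the inclusion of an interaction term between treatment arm and the demographic subgroup". On inference it says: "Contrasts will be used to test for statistically significant differences in the primary outcome hypothesis by subgroup". It says nothing about estimating the STOP/EUC effect inside a subgroup.

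The output is laid out in SAP 18.1, Tables 36-39. Each table has one row per subgroup level. The columns are the number enrolled, the mean (SD) days of risky use in EUC and in STOP, and then a results block headed 'Rate Ratio', 95% lower and upper limits, and p-value. The footnote under all four tables states what the block holds: "The rate ratio and p-value for the interaction term between treatment arm and subgroup is shown". It does not say what the confidence limits belong to.

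The neighbouring tables use the same column heading for something else. In Tables 32-35 and 40 the footnote reads: "The rate ratio is defined as the exponentiated estimate of the treatment effect", that is, STOP relative to EUC.

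Protocol 14.11 commits to subgroup analyses by sex and minority status but gives no output format.

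**The concern.** A ratio in a row labelled with a subgroup, beside that subgroup's two arm means, is naturally read as STOP versus EUC in that subgroup, the more so because the heading has that meaning in the tables on either side. Here it would be the factor by which the treatment effect differs between subgroups. The two quantities have different null interpretations: a treatment ratio of 1 means no effect, whereas an interaction ratio of 1 means the same effect in both groups, however large.

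At stake is whether the subgroup tables answer the question a reader brings to them: how large the estimated effect is in women, in older patients or in Black participants, and how precisely it is known. As planned, the tables give a test of heterogeneity and crude means, but no adjusted effect and no interval for any subgroup.

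**Working it through.** The plan states no figure on this point, so there is none to reproduce. The check compares what the model yields with what the shells can hold.

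**Inputs**
- Model: log link, with treatment, subgroup and their interaction (SAP 7.2.2 and 7.4).
- Levels: sex 2, age 2, race 3, ethnicity 2 (SAP 7.4).
- Planning effect: SAP 10.0, scenario 1, gives 90-day means of 20 and 14, "which translate into 180 day means of 40 and 28 in the two groups". The rate ratio is 28/40 = 0.70.
- A second ratio of 0.90 in one subgroup is my assumption, used only to show how the quantities separate.

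**What the interaction term is.** For a two-level factor S (A = 0, B = 1), omitting site, baseline and the random intercept:

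log mean = b0 + b1·treat + b2·S + b3·treat·S

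- STOP/EUC ratio in A: RR_A = exp(b1)
- STOP/EUC ratio in B: RR_B = exp(b1 + b3)
- Interaction ratio: exp(b3) = RR_B / RR_A

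The footnote puts exp(b3) in the 'Rate Ratio' column. It equals a within-subgroup ratio only in special cases, such as RR_A = 1.

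**Numbers**

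| RR in men | RR in women | Interaction ratio, women/men | Interaction ratio, men/women |
|---|---|---|---|
| 0.70 | 0.70 | 0.70/0.70 = 1.00 | 1.00 |
| 0.70 | 0.90 (assumed) | 0.90/0.70 = 1.29 | 0.70/0.90 = 0.78 |

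In the first line STOP reduces days of use by 30% in both sexes, and the table prints 1.00. In the second, the printed value is 1.29 or 0.78 depending on the reference level, which the shell does not name. Neither is the effect in men or in women.

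**Rows against terms.** A factor with k levels gives k − 1 interaction terms.

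| Factor | Rows | Interaction terms |
|---|---|---|
| Sex | 2 | 1 |
| Age | 2 | 1 |
| Race | 3 | 2 |
| Ethnicity | 2 | 1 |

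There are always fewer terms than rows. For sex, age and ethnicity one ratio could stand for the whole table. For race there are two ratios; the plan does not say which is shown, against which reference group, or whether the p-value is a joint test on 2 degrees of freedom.

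**The SAP's own handling of a parallel case.** In SAP 7.6 the quarterly model has a treatment-by-time interaction, and an ESTIMATE statement combines the treatment and interaction coefficients to give the STOP/EUC ratio within a period. The footnotes to the 90-day tables (Tables 43-44) and to Table 45 describe their ratios as built from the main effect and the interaction together. So the SAP reports the treatment effect within each period, but not within each subgroup.

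**The case against.** The strongest reply is that the inference is sound and disclosed. Testing a treatment-by-subgroup term in the primary model is the proper way to look for heterogeneity, and each footnote says that the interaction is what is displayed. That stands: misreading is a risk, not a certainty, and the test should be kept.

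A reader might infer that the interaction ratio is repeated in every subgroup row. The documents do not show this. In all four shells the placeholders appear only on the first row, and the other rows are blank in every column. A single ratio spanning the rows would be consistent with the footnote for the two-level factors.

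A reader might also infer that subgroup effects are not visible at all. That is too strong: the shells have columns for mean (SD) days by arm within each subgroup level, so a crude ratio can be formed. What is missing is the adjusted ratio and its interval.

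The sentence on contrasts in SAP 7.4 could be read as promising tests of the primary hypothesis within subgroups. Even so, it promises tests, not estimates with intervals, and the shells leave no place for them.

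The footnotes also say that missing values are not imputed, so a reader might infer that the remedy is to refit on the 30 datasets imputed for the primary analysis. That does not follow. The imputation models in SAP 7.2.3 use treatment, site, baseline and the six monthly values. They omit sex, age, race and ethnicity and their interactions with treatment, so imputed values would tend to pull any true interaction towards null.

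Finally, SAP 7.4 cites an NIH requirement for these analyses. The cited source is not available here, so the point does not rest on any required format.

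**Conclusion.** The point holds as a reporting defect. In Tables 36-39 the column headed 'Rate Ratio' holds a ratio of rate ratios, under a heading that means the STOP/EUC effect in Tables 32-35 and 40, and no SAP text or shell plans a model-based STOP/EUC rate ratio with a confidence interval in any subgroup. For race the reported quantity is also undefined.

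The size is best seen in the equal-effect case: a ratio of 0.70 in both sexes would print as 1.00. This takes the 0.70 from the plan's scenario 1 and assumes a homogeneous effect. It illustrates the mislabelling and predicts nothing about the trial's results.

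The consequence is limited. These are supplemental analyses in shells titled as proposed, the interaction test is valid, and the primary test is untouched. It is a worthwhile improvement rather than a threat to the trial's conclusions.

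**What to change.** Keep the interaction model in SAP 7.4 and change what is taken from it:

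- For each subgroup level, use an ESTIMATE statement combining the treatment and interaction coefficients, as SAP 7.6 does for time periods, and print the STOP/EUC rate ratio with its 95% CI in that row. Check the coefficient order against the class-level coding so that the ratio is STOP over EUC.
- Report one p-value per factor, in its own column headed as the interaction p-value: 1 degree of freedom for sex, age and ethnicity, and a joint test on 2 degrees of freedom for race.
- If an interaction ratio is also shown, label it as such and name the reference level.
- Rewrite the footnotes to Tables 36-39 to match, and add a sentence to SAP 7.4 stating that within-subgroup ratios with intervals will be reported.

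Do not move these analyses onto the existing imputed datasets. That would first need imputation models that include the subgroup variables and their interactions with treatment, which is a larger job and is not needed for this correction.

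The cost is four table shells, their footnotes, one sentence of SAP text and a few lines of code. No new data or model is needed.

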11.8.3 RA-recorded ED Visits and Hospitalizations

This form will be used to capture information regarding a participant's ED visit or hospitalization during the course of the study post baseline. The form will document the admission dates of ED visits or hospitalization, the dates that the RC/RA was notified of these visits, diagnoses, outcomes, and discharge dates. The RC/RA is expected to submit this form for every ED visit and hospitalization that they become aware of after the baseline visit.

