14.12 Safety Analysis

All Safety Events will be presented as: (1) the number and proportion of participants experiencing at least one incidence of each event overall and by intervention group; and (2) a table displaying the total number of each event overall and by intervention group. Safety Events that are associated with participant death will be summarized by body system and preferred term using MedDRA codes (per The Medical Dictionary for Regulatory Activities). Listings of death events will be sorted by system organ class (SOC) and preferred term (PT). Concomitant medications of interest will be coded using the World Health Organization Drug Dictionaries (WHO DD) and presented by preferred drug name and WHO Anatomical Therapeutic Chemical (ATC) classification analogous to Safety Event reporting.

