8.3 Hospitalizations

Post-baseline research assistant (RA) collected hospitalizations will be summarized by treatment arm. The number of hospitalizations, the number of patient participants with hospitalizations, and the number of hospitalizations per patient participant (both numerically and categorically (0, 1, 2, 3, 4, and 5 or more visits)) will be presented. A listing of hospitalizations by treatment arm will be generated. The listing will include Site, Participant ID, date of enrollment, date of hospitalization, discharge date, primary, secondary, and tertiary diagnosis/complaint, severity, and outcome.

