8.5 Death

[figure not shown]
A listing of deaths by treatment arm will be presented and will include Site, Participant ID, date of enrollment, date of death, source of death report, primary, secondary, and tertiary cause of death, and MedDRA® coded preferred term and system organ class. Narratives of deaths will also be provided.

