	Number of participants with at least one non-fatal drug or alcohol overdose	N (X.X%)		
	Number of non-fatal drug or alcohol overdoses per participant			
	N	N		
	Mean	X.X		
	SD	X.XX		
	Minimum	X		
	Median	X.X		
	Maximum	X		

Table 66: Summary of Suicide Risk by Treatment Arm Patient Participants			
	Treatment Arm		Total (N=)
	EUC (N=)	STOP (N=)	
Number endorsing suicide risk on PSS ¹ at Baseline	N (X.X%)		
Number endorsing suicide risk on PSS at 6-months	N (X.X%)		
Number endorsing suicide risk on PSS at 12-months	N (X.X%)		
Number endorsing suicide risk on PSS at either 6 or 12-months	N (X.X%)		

¹ Patient Safety Screener. PSS is administered at baseline, 6-months, and 12-months. Endorsing suicide risk on PSS is defined as a response of 'yes' to having thoughts of killing themselves over the last 2 weeks or if they attempted to kill themselves within the last 24 hours (including today) or within the last month (but not today).

Table 67: Summary of Hospitalizations by Treatment Arm				
Patient Participants				
Visit		Treatment Arm		
		EUC (N=)	STOP (N=)	Total (N=)
6-month	Number of hospitalizations	N		
	Numbers of participants with hospitalizations	N (X.X%)		
	Number of hospitalizations per participant			
	0	N (X.X%)		
	1			
	2			
	3			
	4			
	5 or more			
	Number of hospitalizations per participant			
	N	N		
	Mean	X.X		
	SD	X.XX		
	Minimum	X		
	Median	X.X		
	Maximum	X		
12-month	Number of hospitalizations	N		
	Numbers of participants with hospitalizations	N (X.X%)		
	Number of hospitalizations per participant			
	0	N (X.X%)		
	1			
	2			
	3			
	4			
	5 or more			
	Number of hospitalizations per participant			
	N	N		
	Mean	X.X		
	SD	X.XX		
	Minimum	X		
	Median	X.X		
	Maximum	X		

Table 68: Summary of ED Visits by Treatment Arm				
Patient Participants		Treatment Arm		
Visit		EUC (N=)	STOP (N=)	Total (N=)
6-month	Number of ED visits	N		
	Numbers of participants with ED visits	N (X.X%)		
	Number of ED visits per participant			
	0	N (X.X%)		
	1			
	2			
	3			
	4			
	5 or more			
	Number of ED visits per participant			
	N	N		
	Mean	X.X		
	SD	X.XX		
	Minimum	X		
	Median	X.X		
	Maximum	X		
12-month	Number of ED visits	N		
	Numbers of participants with ED visits	N (X.X%)		
	Number of ED visits per participant			
	0	N (X.X%)		
	1			
	2			
	3			
	4			
	5 or more			
	Number of ED visits per participant			
	N	N		
	Mean	X.X		
	SD	X.XX		
	Minimum	X		
	Median	X.X		
	Maximum	X		

Listing 1: Listing of Non-fatal Drug or Alcohol Overdoses by Treatment Arm						

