Patient Participants						
Treatment Arm = EUC/STOP						
Site	Participant ID	Date of Enrollment	Visit	Date of Assessment	Number of Overdoses¹	Comments
xxxxxxxxxx	xxxxxxxxxxxxxx	mm/dd/yyyy	Baseline/ 6-month/ 12-month	mm/dd/yyyy	N	xxxxxxxxxx

¹ Only the number of non-fatal drug or alcohol overdoses in the past 6 months are reported at each visit.

Listing 2: Listing of Suicide Risk by Treatment Arm							
Treatment Arm = EUC/STOP							
Site	Participant ID	Date of Enrollment	Visit	Date of Assessment	Over the past 2 weeks, have you had thoughts of killing yourself?	Have you ever attempted to kill yourself?	If yes, when did this last happen?
xxxxxxxxxx	xxxxxxxxxxxxxx	mm/dd/yyyy	Baseline/ 6-month/ 12-month	mm/dd/yyyy	Yes/ No/ Unable to complete	Yes/ No	Within the last 24 hours (including today)/ Within the last month (but not today)/ Between 1 and 6 months ago/ More than 6 months ago

All visits are included for participants who answered 'yes' to having thoughts of killing themselves over the last 2 weeks or if they attempted to kill themselves within the last 24 hours (including today) or within the last month (but not today).

Listing 3: Listing of Hospitalizations by Treatment Arm
Patient Participants

Treatment Arm = EUC/STOP

Site	Participant ID	Treatment Arm = EUC/STOP					Severity	Outcome
		Date of Enrollment	Date of Hospitalization	Date of Discharge	Primary Diagnosis/ Complaint	Secondary Diagnosis/ Complaint	Tertiary Diagnosis/ Complaint	
xxxxxxxxxx	xxxxxxxxxxxx	mm/dd/yyyy	mm/dd/yyyy	mm/dd/yyyy	xxxxxxxxxx	xxxxxxxxxx	xxxxxxxxxx	Recovering/resolving/ Recovered/resolved/ Recovered/recovered with sequela/ Not recovered/not resolved/ Fatal/ Unknown

All hospitalizations are as reported on the ED Visits and Hospitalization (EDH) form.

Listing 4: Listing of ED Visits by Treatment Arm
Patient Participants

Treatment Arm = EUC/STOP						
Site	Participant ID	Date of Enrollment	Date of ED Visit	Date of Discharge	Primary Diagnosis/ Complaint	Secondary Diagnosis/ Complaint
xxxxxxxxxx	xxxxxxxxxxxxxx	mm/dd/yyyy	mm/dd/yyyy	xxxxxx	xxxxxxxxxx	xxxxxxxxxx

All ED visits are as reported on the ED Visits and Hospitalization (EDH) form.

Treatment Arm = EUC/STOP							MedDRA vxx.x	
Site	Participant ID	Date of Enrollment	Date of Death	Source of Death Report	Type	Cause of Death	MedDRA vxx.x	
							Preferred Term	System Organ Class

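### Safety Tables 65, 67 and 68 count affected participants only within separate visit blocks, so the shells omit the whole-follow-up count by arm that Protocol 14.12 requires

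*SAP*

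**What the plan says.** **Protocol 14.12** sets two results for all Safety Events: "the number and proportion of participants experiencing at least one incidence of each event overall and by intervention group", and "a table displaying the total number of each event overall and by intervention group". It mentions no split by visit. The Safety Events are overdoses, suicidal ideation, hospitalizations, ED visits and deaths (Protocol 15.16, SAP 3.3.5).

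**SAP text.**
- Section 8.1 collects self-reported overdoses over the past 6 months at baseline, 6 and 12 months, and ties the summary to each visit.
- Section 8.3 says: "Post-baseline research assistant (RA) collected hospitalizations will be summarized by treatment arm". Section 8.4 does the same for ED visits. Both plan the number of participants affected, and neither mentions visits.
- Section 8.5 says: "A listing of deaths by treatment arm will be presented". It adds narratives.

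**SAP shells (Appendix 18.1).**
- Table 65 (overdoses) has Baseline, 6-month and 12-month blocks.
- Tables 67 and 68 (hospitalizations, ED visits) have a Visit column with 6-month and 12-month blocks. In Table 67 the participant row is "Numbers of participants with hospitalizations".
- Table 66 (suicide risk) alone ends with a combined row: "Number endorsing suicide risk on PSS at either 6 or 12-months".

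**Data source for Tables 67 and 68.** Listing 3 notes: "All hospitalizations are as reported on the ED Visits and Hospitalization (EDH) form". Listing 4 says the same of ED visits. Protocol 11.8.3 says of that form: "The RC/RA is expected to submit this form for every ED visit and hospitalization that they become aware of after the baseline visit". Protocol Table 6 schedules it as needed.

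**The concern.** The protocol asks for one figure per event and arm: how many people were affected during follow-up. A participant with events in both halves of the year appears in both blocks of Table 67, so the two block counts do not give that figure. A reader who adds them may count people twice, and a reader who quotes one block reports half the follow-up.

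In Tables 67 and 68 there is a second problem. The source form is triggered by an event and carries dates, not a visit. Without an assignment rule, two programmers could fill the blocks differently.

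These are the trial's planned by-arm safety summaries. Two arms could show identical tables while different numbers of people had been hospitalized.

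**Working it through.** The plan states no figure to reproduce, so the check has two parts.

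**1. Requirement against output**

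| Event | SAP text | Shell | Combined post-baseline participant row |
|---|---|---|---|
| Overdose | 8.1: at each visit | Table 65: Baseline, 6-month, 12-month | Neither in text nor in shell |
| Suicide risk | 8.2: each visit, plus either 6 or 12 months | Table 66 | Yes |
| Hospitalization | 8.3: one post-baseline summary | Table 67: 6-month, 12-month | In text, not in shell |
| ED visit | 8.4: one post-baseline summary | Table 68: 6-month, 12-month | In text, not in shell |

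Neither Table 67 nor Table 68 states a date window, an assignment rule, or whether the 12-month block starts at baseline.

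**2. Can the whole-follow-up count be recovered from the blocks?**

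Let *a* and *b* be the participants with at least one event in each of two non-overlapping blocks, *c* those with events in both, and *N* the arm size. Then

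participants with any event = *a* + *b* − *c*, so max(*a*, *b*) ≤ any event ≤ min(*a* + *b*, *N*).

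The shells print *a* and *b* but not *c*. For illustration take *N* = 150. This is an assumption: half of the approximately 300 patients, although a cluster-randomized trial need not split evenly. The values of *a* and *b* are also assumed.

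| *a* + *b* | Any event | Percent of 150 |
|---|---|---|
| 5 + 5 | 5 to 10 | 3.3% to 6.7% |
| 15 + 15 | 15 to 30 | 10.0% to 20.0% |
| 15 + 25 | 25 to 40 | 16.7% to 26.7% |
| 30 + 30 | 30 to 60 | 20.0% to 40.0% |

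With equal blocks the uncertainty is a factor of two. If events in the two halves were independent, 15 + 15 would give 150 × (1 − 0.9 × 0.9) = 28.5 people.

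A concrete pair, with one event per affected participant in each block:
- Arm 1 has 12 people with events in both halves: 15 + 15 − 12 = 18 affected (12%).
- Arm 2 has none in both: 15 + 15 − 0 = 30 affected (20%).

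Both arms would print the same Table 67, including total events (15 per block) and the per-participant distribution within each block.

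Total events, the protocol's second result, can be summed across non-overlapping blocks. Only the participant count is lost.

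**The case against.** The strongest reply is that this is a mismatch in shells labeled as proposed, and that the result is not missing from the plan. Much of that stands.

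- **Hospitalizations and ED visits.** A reader might infer that these results are never produced. The documents do not support that, because SAP 8.3 and 8.4 commit to the unsplit post-baseline participant count. The defect is a conflict between text and shell.
- **Cumulative reading.** If the 12-month block in Tables 67 and 68 runs from baseline, it is the required count. Nothing says so, and Table 65, laid out the same way, is titled as covering the past 6 months.
- **Listings.** Listings 1, 3 and 4 carry participant IDs by arm, so the count can be derived by hand. For Listing 1 that means setting aside people who reported an overdose only at baseline. This is still not the tabulated number and proportion that the protocol asks for.
- **Table 65.** Visit blocks suit an instrument given at fixed visits with a 6-month recall. The difficulty with as-needed records is confined to Tables 67 and 68.
- **Deaths.** A reader might infer that deaths receive only a listing. In fact SAP 8.5 adds narratives, Tables 16 and 17 count death as a termination reason (Table 17 by arm), and SAP 7.10 gives proportions of fatal overdoses by arm.
- **Other views of harm.** A reader might take these tables as the only by-arm look at harm. They are not: SAP 7.8 compares arms on moderate-severe OUD, overdose, pain, depression and suicidality, and self-reported ED and hospital use.

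The magnitudes above are bounds under assumed counts, not expected discrepancies.

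**Conclusion.** The point holds in a limited form. As drawn, Tables 65, 67 and 68 do not deliver the by-arm count of participants with at least one post-baseline event that Protocol 14.12 requires. The gap is clearest for overdoses, where the SAP text does not supply the count either. For hospitalizations and ED visits it is an unresolved conflict between SAP 8.3–8.4 and the shells, plus an undefined visit split.

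Under non-overlapping blocks of equal size, the number of people affected can differ by up to a factor of two from what either block shows: 15 to 30 of an assumed 150 in the illustration. No actual event rate is known from the documents.

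The primary analysis and data collection are unaffected. The change is still worth making, because following the shells literally leaves out a result the protocol promised, and Table 66 shows that the row was thought of for one event type.

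**What to change.** - **Tables 65, 67 and 68:** add an any-time-post-baseline row with the number and percentage of participants with at least one event, and the total events, by arm and overall. In Table 65 this follows the pattern of Table 66 and excludes the baseline report.
- **SAP 8.1:** name the combined overdose count in the text, so that text and shell agree.
- **Tables 67 and 68:** either drop the Visit column, in line with SAP 8.3 and 8.4, or define the blocks by event date (study-day windows) and state whether the 12-month block is cumulative.
- **Optional:** add a safety-population count and percentage of all deaths by arm. Tables 16 and 17 record death only as a reason for termination.

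Protocol 14.12 does not require follow-up time in these tables, so it need not be added. The cost is a few lines of shell and text. All dates and responses are already collected, and no other analysis changes.
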